### 10.3 Vital Signs

Vital signs collected at Screening will be presented as baseline characteristics using descriptive statistics. All vital signs results will be listed.

## 11 Other Analyses

No other analyses planned. All other data collected in the eCRF will be only listed.

## 12 Changes in the Planned Analyses from Study Protocol

- The protocol Section 12.2 describes the FAS as “the primary analysis set for all efficacy analyses”. The first secondary objective is “to demonstrate the non-inferiority of CUSA-081 compared to alteplase in the rate of treatment success following a single administration with a dwell time up to 90 minutes”. The primary analysis corresponding to this objective, which is included within the hierarchical closed testing procedure, will be based on the Per-Protocol Set, since this approach is considered as more conservative as per Section 5.2.3 of ICH E9. The FAS will be the primary analysis set for all efficacy analyses involving assessment of superiority.
- The protocol Section 12.3.7 describes an interim futility analysis. Since the study has been terminated by the Sponsor prematurely for other reasons, the futility analysis will not be conducted. The analysis to be conducted following the premature closure of the study will be exactly the analysis which is planned for end of study. The database lock and unblinding will be conducted according to the relevant SOPs of the Sponsor and CRO and the analysis conducted will be considered as the final study analysis.
- The definition of the Per-Protocol Set has been modified to use Safety Set instead of ITT Set in order to include in the Per-Protocol Set only treated subjects.

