12.2 Populations for Analysis

- **Full analysis set (FAS):** All randomized subjects who receive at least one dose of study drug, and with at least one available evaluation of efficacy after baseline. Analyses using the FAS set will be based on the treatment randomized. The FAS will be the primary analysis set for all efficacy analyses.
- **Safety set (SS):** All randomized subjects who receive at least one dose of study drug. Subjects discontinued after dosing will be part of the SS. Analyses based on the SS set will be based on the actual treatment received. The SS will be the primary analysis set for all safety analyses.
- **ITT analysis set (ITT):** All randomized subjects regardless if they received treatment with study drug. The ITT will be based on the randomized treatment allocation. The ITT will be used for sensitivity analysis for the primary efficacy analyses.
- **Per-protocol analysis set (PPS):** all subjects from the ITT set without any important protocol deviations. Important protocol deviations are a subset of protocol deviations that may significantly impact the completeness, accuracy, and/or reliability of key study data or that may significantly affect a subject's rights, safety, or well-being. Important protocol

 Chiesi	Clinical Study Protocol
Clinical Study Code No.: CUSA-081-HEM-01	Version No.: 8.0
EUDRACT No./IND No.: 2019-002124-32/128551	Date: 21 FEB 2023

deviations will be assigned in a blinded manner prior to database lock. The PPS will be used for sensitivity analysis for the primary efficacy analyses and the non-inferiority analyses.

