## 5 Sample Size

For the primary assessment of the superiority of CUSA-081 vs. placebo, a sample size of 450 in the active arm (CUSA-081), and 50 in the control arm (placebo), will provide >99% power to detect a difference of  $\geq 35\%$  using a two-sided test at significance level of 0.05. The expected placebo response rate is approximately 20%.

For the assessment of the non-inferiority of CUSA-081 vs alteplase, a sample size of 450 in the active arm (CUSA-081), and 300 in the control arm (alteplase) will provide 87% power at the 2.5% significance level (that is by using one-sided 97.5% confidence intervals (CI)) with a non-inferiority margin of -10%, assuming an equal response rate of 75% in the control arm (alteplase), and the active (CUSA-081) arm. A sample size of 450 in the active arm (CUSA-081), and 300 in the control arm (alteplase) will also provide 92% power to detect a difference of 10% between the success rates using a two-sided test at significance level of 0.05.

A minimum of 841 subjects will be randomized in order to achieve a minimum of 800 subjects completing the study.

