## 6.4 Per-Protocol Analysis Set (PPS)

All subjects from Safety Set without any important protocol deviations. Important protocol deviations are a subset of protocol deviations that may significantly impact the completeness, accuracy, and/or reliability of key study data or that may significantly affect a subject's rights, safety, or well-being. Important protocol deviations will be assigned in a blinded manner prior to database lock. The PPS will be used for sensitivity analysis for the primary efficacy analyses and the non-inferiority analyses.

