# 7 General Considerations for Statistical Analysis

## 7.1 Statistical Significance

All tests of superiority hypotheses will be two-sided and conducted at the 0.05 significance level, and all confidence intervals will be two-sided at the 95% confidence level.

The assessment of non-inferiority will be based on the 2.5% level of significance (using one-sided 97.5% confidence intervals) with a non-inferiority margin of -10%.

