### Non-Inferiority Hypotheses

The hypotheses for the non-inferiority are as follows:

The null hypothesis H0:  $R_c - R_a \leq -10$   
The alternative hypothesis H1:  $R_c - R_a > -10$

Where Rc=Rate of success of CUSA-081  
Ra=Rate of success of alteplase

Assessment of non-inferiority will be based on the 95% confidence interval for the difference in the rate of treatment success between CUSA-081 vs alteplase following a single administration with a dwell time up to 90 minutes.

Non-inferiority will be demonstrated (or null hypothesis will be rejected) when the lower limit of the 95% confidence interval for the difference in rate of success is greater than -10% (See Section 14.1).

The number and percent of subjects with treatment success by treatment group and time point will be summarized. The rate difference and associated 95% Wald confidence intervals between CUSA-081 and placebo or alteplase will be estimated. The between treatment comparisons will be performed using a 2-sample z test for proportions.

For superiority hypotheses, the primary analysis will be the analysis performed on the FAS. Analyses will be repeated based on the ITT and PP Sets as sensitivity analyses. For non-inferiority hypotheses, the analysis based on the PP Set will be considered as the primary analysis.

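### The confirmatory non-inferiority conclusion rests on the Per-Protocol Set alone, with no role for the FAS and with conflicting set labels in the SAP

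*SAP*

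**What the plan says.** Protocol 12.2 states: "The FAS will be the primary analysis set for all efficacy analyses". It gives the PPS a sensitivity role. SAP section 12 declares a change for the first secondary objective, CUSA-081 vs alteplase at 90 minutes: "The primary analysis corresponding to this objective, which is included within the hierarchical closed testing procedure, will be based on the Per-Protocol Set", because the PPS is considered more conservative under ICH E9. SAP 9.1 follows: "For non-inferiority hypotheses, the analysis based on the PP Set will be considered as the primary analysis". SAP 6.3 limits the FAS to superiority assessments.

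Other parts of the SAP do not match:

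- Section 6.4 carries over the protocol sentence: "The PPS will be used for sensitivity analysis for the primary efficacy analyses and the non-inferiority analyses".
- Section 9 opens by placing all efficacy comparisons on the FAS, then makes the PPS primary for NI in its next sentence.
- Table 14.2.1.3.1, which would hold the deciding PPS result, is titled a sensitivity analysis.
- Section 7.2.1 stops the hierarchy on a single lower confidence limit and names no set.

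NI is shown "when the lower limit of the 95% confidence interval for the difference in rate of success is greater than -10" percent. No section says what follows if the PPS passes and the FAS fails.

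**The concern.** The FAS is analysed as randomised, although it requires a dose and one post-dose assessment. The PPS also drops subjects for events after randomisation; SAP 7.11.2 lists incomplete dosing and non-permitted medication. In this design those events can be related to outcome. Successes leave the treatment algorithm (Protocol 7.1.1), while subjects not restored at 90 minutes go on to a second syringe within a 15-minute limit and to further timed assessments, so failures have more opportunity to deviate. A missing assessment before success counts as failure (SAP 7.3). If that omission is judged an important deviation, a FAS failure may disappear from the PPS.

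As written, NI would be claimed and testing would continue even with a FAS lower limit at or below -10%. A disagreement between the sets would then be argued after unblinding.

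**Working it through.** **Inputs.** Margin -10 points and one-sided 2.5% (SAP 7.1); Wald interval (SAP 9.1 and 14.1); and from SAP 5, "a sample size of 450 in the active arm (CUSA-081), and 300 in the control arm (alteplase) will provide 87% power", "assuming an equal response rate of 75% in the control arm (alteplase), and the active (CUSA-081) arm". The documents give no expected PPS size, so every exclusion share below is an assumption.

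**Formula.** P(claim NI) = Φ((p1 - p2 + 0.10)/SE - 1.96), with SE = √(p1(1-p1)/n1 + p2(1-p2)/n2). Arm 1 is CUSA-081 and arm 2 is alteplase.

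**The plan's own figure.** SE = √(0.1875/450 + 0.1875/300) = 0.03227. Then 0.10/0.03227 = 3.098, and Φ(3.098 - 1.96) = 87.3%. The stated 87% reproduces.

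**False NI rate.** Take true FAS rates on the null boundary, 65% vs 75%, with 450/300. Removing failures equal to a share e of an arm changes its rate p to p/(1-e) and its size n to n(1-e).

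| Assumed exclusions | PPS rates | P(claim NI) |
|---|---|---|
| Non-informative | 65.0% vs 75.0% | 2.5% |
| Failures equal to 1% of each arm | 65.7% vs 75.8% | 2.3% |
| Failures equal to 2% of each arm | 66.3% vs 76.5% | 2.2% |
| Failures equal to 3% of each arm | 67.0% vs 77.3% | 2.0% |
| 2% of the failures in each arm | 65.5% vs 75.4% | 2.6% |
| 5% of the failures in each arm | 66.2% vs 75.9% | 2.9% |
| 10% of the failures in each arm | 67.4% vs 76.9% | 3.4% |
| CUSA-081 failures only, 1% of that arm | 65.7% vs 75.0% | 3.9% |
| CUSA-081 failures only, 2% of that arm | 66.3% vs 75.0% | 5.9% |
| CUSA-081 failures only, 3% of that arm | 67.0% vs 75.0% | 8.7% |

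For the last row, p1 = 0.65/0.97 = 0.6701 and n1 = 436.5, so SE = 0.03364, and Φ(0.0201/0.03364 - 1.96) = Φ(-1.362) = 8.7%. Equal shares of each arm widen the difference slightly. An equal fraction of failures narrows it, because the arm with more failures loses more of them.

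**How few subjects can matter.** FAS 315/450 (70.0%) vs 225/300 (75.0%) gives -5.0 - 1.96 × 3.30 = -11.5%, which fails. Dropping 10 CUSA-081 failures (2.2% of the arm) gives 315/440 = 71.6%, and -3.41 - 1.96 × 3.30 = -9.9%, which passes.

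**Requiring both sets.** A joint rule cannot reject more often than the FAS test alone. In 400,000 simulated trials with only CUSA-081 failures excluded (3% of the arm), the false NI rate was 8.4% on the PPS alone and 2.4% when both sets were required.

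**Power cost.** Treat the two test statistics as bivariate normal with correlation √f, where f is the PPS share of the FAS, with random exclusions and 75% in both arms.

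- 450/300, f = 0.90: 83.6% on the PPS alone, 82.2% on both.
- 450/300, f = 0.95 and 0.80: 85.5% vs 84.3%, and 79.1% vs 77.5%.
- 234/156 (416 × 9/16 and 416 × 6/16, an assumed size after early stopping), f = 0.90: 56.3% vs 53.3%.

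**The case against.** The case for leaving the plan alone has real weight.

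- **Blinding.** Important deviations are assigned blind before database lock (SAP 6.4), set membership is agreed in blind review (SAP 6), and exclusions are documented before unblinding (SAP 7.11.2). This rules out deliberate selection by arm. What remains is deviation frequency that differs by outcome or treatment, and no document shows that it would differ between two blinded thrombolytic arms on the same schedule.
- **A declared, reasoned choice.** Section 12 names the protocol text that it changes. The FAS ignores protocol violations and counts missing assessments as failures, which can shrink a difference between active arms. That supports the PPS as a useful analysis, but not as the only one.
- **Datapoint exclusions.** SAP 7.11.2 allows a deviation affecting one datapoint to remove only that datapoint, so a second-dose problem need not remove the 90-minute result. This narrows the mechanism without closing it.
- **Visibility.** The FAS and ITT comparisons with alteplase are tabulated, so disagreement would be seen. It would still have no bearing on the decision.

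A reader might infer that a false pass at this step undermines every later confirmatory claim. The documents do not support that, because the later steps are superiority tests with the FAS as primary set. A drug with 65% success at 90 minutes would still be 45 points above the expected placebo rate of about 20%, so the placebo claims would be unlikely to be false. For superiority over alteplase at a true -10 points, Φ(-0.10/0.0336 - 1.96) is about 4 in 10 million.

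**Conclusion.** The gap is real and modest. One set decides a confirmatory claim, no rule covers disagreement, and the SAP labels that set inconsistently. The label conflict is editorial and cannot itself create a false claim, since SAP 6.3, 9.1 and 12 agree on the PPS for NI.

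It would be tempting to conclude that per-protocol exclusions more than double the error rate. That holds only in the one-sided pattern, from roughly 2% of the CUSA-081 arm upward. The two-sided patterns examined stay between 2.0% and 3.4%, and random exclusions leave the rate at 2.5%. This is a vulnerability under assumed exclusion patterns, not a demonstrated bias. Its consequence falls mainly on the NI claim itself.

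**What to change.** Before unblinding, state in SAP 7.2.1 and 9.1 that NI is concluded, and testing continues, only if the lower limit of the 95% interval exceeds -10% in both the PPS and the FAS. Align SAP 6.4, the opening of SAP 9 and the title of Table 14.2.1.3.1 with that rule.

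This needs wording only, because both comparisons are already planned (Tables 14.2.1.1.1 and 14.2.1.3.1). The price is the lost NI power calculated above: small at planned size, and larger in absolute terms if early termination leaves a much smaller trial. Restating planned power for the PPS would add little now that the study has been stopped early.

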## 13 Output

### 13.1 Software

SAS version 9.4 will be used to perform all the statistical analyses.

### 13.2 Reporting Conventions

#### 13.2.1 Treatment, Visit and Subgroup Descriptors

In the tables, listings and figures, the treatments, visits and timepoints will be identified as described below.

Treatment group (as displayed in outputs)	Descriptor for treatment
CUSA-081	One or two doses of “CUSA-081” (reteplase)
Placebo	One or two doses of “Placebo” (normal saline)
Alteplase	One or two doses of “alteplase”

Output	Descriptor for visits
Tables	Baseline Visit (Day 0 or Day 1) Visit 1 (Day 1) Follow-up Visit 2 (Day 30)  Timepoints will be presented as 30 mins, 60 mins, 90 mins, 120 mins, 150 mins and 180 mins.
Listings	Baseline, Visit 1 and Visit 2 will be presented in the “Visit” column.  Timepoints will be presented as 30 mins, 60 mins, 90 mins, 120 mins, 150 mins and 180 mins.
Figures	Baseline, Visit 1 and Visit 2  Timepoints will be presented as 30 mins, 60 mins, 90 mins, 120 mins, 150 mins and 180 mins.

Subgroup	Category descriptor
Age	
 
• <18 years
 
• ≥18-<65 years
 
• ≥65-<85 years
 
• ≥85 years
 

Sex	
 
• Male
 
• Female
 

BMI	
 
• <18.5 kg/m^2
 
• ≥18.5-<25 kg/m^2
 
• ≥25.0-<30 kg/m^2
 
• ≥30.0 kg/m^2
 

Country	
 
• All countries to be included in full text.
 

Region	
 
• US
 
• Non-US
 

Type of CVAD	
 
• Non-tunneled or Tunneled Central Venous Catheter (CVC)
 
• Implanted Ports
 
• Peripherally Inserted Central Catheters (PICCs)
 

Number of lumens	
 
• Single lumen
 
• Multi-lumen: 2
 
• Multi-lumen: 3
 
• Multi-lumen: 4
 

Where and by whom was the CVAD identified as dysfunctional	
 
• Patient/caregiver identified
 
• Healthcare provider not at study site
 
• Healthcare provider at study site
 

Duration of CVAD dysfunction	
 
• 0-5 hours
 
• >5-48 hours
 

Race	
 
• American Indian or Alaska Native
 
• Asian
 
• Black or African American
 
• Native Hawaiian or Other Pacific Islander
 
• White
 
• Other
 
• Not Reported
 
 
In case of multiple races for a same subject, the combination of the races will be displayed as a new category.

Ethnicity	
 
• Hispanic or Latino
 
• Not Hispanic or Latino
 
• Not Reported
 
• Unknown
 

### 13.2.2 Decimal Places

Quantitative variables will be listed with the same number of decimal places as in the actual data.

The following rules on decimal places will be considered in the listings for the derived variables (in the analyses rounding will not be performed):

Variables	Decimal Places

 
Duration of AE, medication (days)
 
Time to first re-occlusion (days)
 
	0 decimal

 
BMI (kg/m^2)
 
Time between screening CVAD assessment and first drug administration (hours)
 
Duration of CVAD dysfunctional (hours)
 
	1 decimal

The following rules on decimal places will be considered for the results of the analyses (if the analyses are performed on derived variables, the level of precision of the actual data is derived from the previous list):

All summary statistics will be rounded (using the SAS® function ROUND) and wherever possible data will be decimal aligned.

Statistic	Number of decimal places for reporting
Counts (n)	None
Percentages (%)/Proportion	1 decimal place Note: If the calculated percentage is >0.0% but <0.1% then <0.1% is to be presented in the relevant table and/or listing. If the calculated percentage is >99.9% but <100.0% then >99.9% is to be presented in the relevant table and/or listing.
Mean, Median, SD, 25 th percentile, 75 th percentile, Confidence intervals, Kaplan-Meier estimate	Actual data + 1 decimal place
Probability of re-occlusion free	3 decimals
Difference between percentages (%)/Proportions	Actual data + 1 decimal place
Min, Max	Same as actual data
Odds-ratio and its confidence limits	3 decimals
p-values	3 decimal places. Note: If the p-value is less than 0.001, it will be presented as <0.001. If the rounded result is a value of 1.000, it will be displayed as >0.999.

### 13.2.3 Other Reporting Conventions

Treatments will be presented with the following order in the tables: CUSA-081, Placebo, Alteplase.

In general, dates will be presented on listings in the format ddmmyyyy (date9.) and time in the format hh:mm (time5.). In case of partial dates or times, missing information will be replaced by dashes.

In the listings, a unit associated with a variable will be presented only once within parentheses either below or next to that variable in the heading portion. If a parameter has multiple units, each unit will be displayed only once, as applicable.

All tables will have their source listing referenced in a footnote. All figures will include the source table in a footnote. Listings should be sorted by subject ID and visit (unless otherwise specified) and have the SDTM and/or ADaM source data referenced in a footnote. The columns of each listing should fit into one page and should not be split into different pages.

When an output is split in multiple pages, page-break should be adequately controlled.

When a table is split in multiple pages, breaking of a block information in different pages is not allowed.

In a listing, in the case that a subject's record has been continued to the next page, an appropriate identification (e.g., the subject ID number and any other relevant information which is split between 2 pages) must be presented at the beginning of that page.

When a listing contains a lot of information, in order to optimize space on the page, some columns can be merged (e.g. "reported term" and "indication" may be presented in the same column).

## 13.3 Format

The following information should always be presented:

- 'Clinical Study Code No.:<Study Code No.>' followed by Chiesi denomination in the top portion of each page. Chiesi denomination is 'Chiesi Farmaceutici S.p.A'.
- The table/listing/figure number followed by the title, the analysis set used and the output page number in the format of 'Page x of Y' in the top portion of each page of any table/listing/figure.
- The SAS program name followed by the datetime of the output production and the analysis type (e.g. Dry Run; Draft Version; Final Version) in the bottom portion of each page of any table/listing/figure. The source listing/table/dataset will appear bottom left for every table/figure/listing.
- Tables and listings will be produced in rich text format (i.e., they will be tabular in format). Individual outputs must be provided in both portable format document (.pdf) and rich text format (.rtf).
- Combined PDF and RTF documents must also be provided, including a table of contents with hyperlinks. The combined documents should be divided by document type (tables, figures, listings).

- SAS outputs will be provided to the Sponsor in a similar manner (PDF and RTF; combined and with hyperlinked table of contents). The SAS outputs will be a separate deliverable to the Sponsor and are not intended for inclusion within the CSR.
- The combined documents page number in the format of ‘Page n of N’ will be presented bottom right corner.

The following should be followed for the tables:

- A landscape layout and Letter size will be used.
- A 9-point font size will be used using Courier New font.
- Horizontal lines will appear before and after the column heading of the output.
- Additional footnotes may be included if strictly necessary for clarification. Footnotes will be put under the main body of text at the bottom left of the page and will be displayed on each page of the output and not only on the last one.
- The left and right margins will be a minimum of 2.1 cm from the left and 1.9 cm from the right. The top and bottom margins will be a minimum 2.92 cm. Header and footer will be both 1.27 cm.

The following should be followed for the listings:

- A landscape layout and Letter size will be used.
- An 8-point font size will be used using Courier New font.
- Horizontal lines will appear before and after the column heading of the output.
- Additional footnotes may be included if strictly necessary for clarification. Footnotes will be put under the main body of text at the bottom left of the page and will be displayed on each page of the output and not only on the last one.
- The left and right margins will be a minimum of 2.1 cm from the left and 1.9 cm from the right. The top and bottom margins will be a minimum 2.92 cm. Header and footer will be both 1.27 cm.

The following should be followed for the figures:

- A portrait layout and Letter size will be used.
- A 9-point font size will be used using Courier New font.
- Figures will be produced in RTF and PDF formats (as described above), including relevant titles and footnotes as separate elements on the page (not within the body of the figure).
- Additional footnotes may be included if strictly necessary for clarification. Footnotes will be put under the main body of text at the bottom left of the page and will be displayed on each page of the output and not only on the last one.

- The size of the figures will be: width=16.3 cm, height=12.2 cm. The resolution will be set using the option IMAGE\_DPI=400. Figures will have a footer specifying the source table or listing. Figures should clearly identify each treatment arm and require care of colors/symbols.
- The left margin will be a minimum of 2.5 cm, the right margin will be a minimum of 2 cm. The top and bottom margins will be a minimum of 0.8 cm.

